2.3 Procedure: Phase II and III (Aim 3- Randomized Controlled Trial) (n=120)

Randomized Controlled Trial Overview: We propose a prospective RCT in which groups of YBMSM will implement a novel intervention with the goal of enhancing social capital and engagement in care among YBMSM living with HIV. Sixty of our participants will be randomized to the treatment arm (divided into at least 6 groups) and participate in the social capital intervention, while the other 60 will be randomized to a group-based health promotion intervention (divided into at least 6 groups) that does not explicitly aim to build social capital (Health for life, or “H4L”). (See Figure 3) Each of the 6 groups in the treatment arm will implement the same intervention. Six groups are necessary in order to ensure that each group has no more than 10 individuals, ensuring that groups are neither too small nor too big. Each of the 6 groups in the group-based health promotion intervention arm will also complete the same curriculum. We will measure social capital using our Modified Social Capital Scale (MSCS; Appendix F, Section 2) at baseline, immediately after completing the intervention (approximately 1 month) and at 4 and 10 months after beginning the intervention. We will also abstract clinical data from electronic medical records at these time points in order to quantify any effect on our care engagement outcomes.

Overview--Intervention Arm: The social capital intervention will be implemented according to the detailed guidelines and manual developed in Phase I above. We will plan for our intervention (and our control condition) to be delivered in either a one day or consecutive two day group meeting at Emory University Rollins School of Public Health or another agreed upon location, at mutually convenient times for the participants. Staff members will be flexible in case evening or weekend meeting times are more convenient for the study participants. The exact number of sessions and

format of the intervention may be modified based on YCAB input; it may be that the intervention can be delivered in fewer sessions, or in a retreat format, to enhance acceptability and retention.

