Retention Plan: Our previous experiences have demonstrated the need to pay careful attention to participant retention: part of the role of the study staff is to remind participants about intervention sessions and study visits, scheduling, and discussing any issues they face in the trial procedures. In [name] ongoing work with the Metropolitan Atlanta Community Adolescent Rapid Testing Initiative (MACARTI) trial, these procedures have resulted in at least an 87% retention among participants who were primarily HIV-positive YBMSM (and may be higher as the follow-up period has not yet ended).

Clinical Outcome Measures: Viral load values and appointment attendance will be extracted from the participants' electronic medical records (EMR). The goal is to abstract measures that correspond to the 0 month (baseline) and 10 month (long term follow-up) time points at which participants will be completing surveys. However, we recognize that lab tests (CD4, VL) in the clinical setting may not necessarily be conducted at a time that corresponds to the survey time point. In light of this limitation, and to make the procedures more uniform, we plan the following: (1) the baseline viral load will be the most recent measurement preceding study participation. If this is >6 months prior to the date of enrollment, this will be considered a missing value. (2) The 10 month viral load will be the first value drawn on or after the date that is exactly one year from the beginning of study participation. If this test is done >6 months after the target date, it will be treated as a missing value.

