4.1 VARIABLES/INTERVENTION

4.2 Variables

Table 2: Variables and Measures

	Method of Measurement	Number of items	Timeline
Social Capital (Primary Outcome)	Modified Social Capital Scale (based on Chen, et al.) ¹⁶	10	Phase I: Analysis of previously collected data Phase III: RCT participants at 0, 1, 4 and 10 months

	Qualitative Interviews	n/a	Phase I: In-depth interviews with YBMSM living with HIV Phase III: Pre- and post-intervention interviews
Engagement in HIV Care (Secondary Outcomes)			
Viral load suppression	Electronic medical record abstraction	n/a	Phase III: RCT participants at baseline, post-intervention and 10 months (if available; see page 17 for more detail)
Retention in Care	Electronic medical record abstraction	n/a	Phase III: RCT participants at 0 and 10 months
Antiretroviral adherence	Single item self-report ⁵²	1	Phase III: RCT participants at 0 and 10 months
Correlates (measuring other factors shown to relate to engagement in care among YBMSM in prior work)			
CD4 count (recent and nadir)	Electronic medical record abstraction	n/a	Phase III: RCT participants at baseline and post-intervention 10 months (if available; see page 17 for more detail)
Demographics	Survey questions	23	Phase III: RCT participants at 0, 1, 4 and 10 months
Depression	CES-D ⁵³	20	Phase III: RCT participants at 0, 1, 4 and 10 months
HIV Stigma	HIV Stigma Scale ⁵⁴	10	Phase III: RCT participants at 0, 1, 4 and 10 months
Ethnic Identity	Multi-Ethnic Identity Measure ⁵⁵	12	Phase III: RCT participants at 0, 1, 4 and 10 months

Gay Identity	Internalized Homonegativity Inventory ⁵⁶	23	Phase III: RCT participants at 0, 1, 4 and 10 months
Drug Abuse	CAGE-AID ⁵⁷	4	Phase III: RCT participants at 0, 1, 4 and 10 months
Social Support	Zimet's Multidimensional Social Support Scale ⁵⁸	12	Phase III: RCT participants at 0, 4 and 10 months
Group Dynamics	Selected items from Schulz, Israel and Lantz ⁵⁹	20	Phase III: RCT participants at 0, 1, 4 and 10 months
Social Networks	Lubben Social Network Scale	6	Phase III: RCT participants at 0, 4 and 10 months
Engagement with Health Care Provider	HCP Scale	13	Phase III: RCT participants at 0, 4 and 10 months
Identification and Involvement With the Gay Community	Identification and Involvement With the Gay Community Scale	8	Phase III: RCT participants at 0, 1, 4 and 10 months
General Wellbeing	The General Well-Being Schedule (GWB)	18	Phase III: RCT participants at 0, 1, 4 and 10 months

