Phase 1- In-depth interviews with YBMSM and key informants: All interviews will take place in a private and quiet room within the IDP clinic or in the case of key informants, at the location of their choosing. [name] has extensive experience conducting such interviews in the clinic for prior research studies and has found this location to be acceptable and comfortable for participants. Interviews will be conducted by a graduate research assistant who will be trained in qualitative methods and interviewing techniques. All interviews will be digitally recorded for subsequent professional transcription. Written informed consent will be obtained before beginning the interview. Interviews will be expected to last approximately 60-90 minutes each. All digitally recorded data will be transcribed verbatim by a professional business transcription service. Qualitative data will be de-identified during this transcription process. Transcripts will then be uploaded into the

MaxQDa qualitative data management software (VERBI Software, Berlin, Germany) for further processing and analysis.

Phase 1- social capital surveys: this data was collected as part of our pilot work prior to the award period. It has already been de-identified and is ready for analysis.

Phase 2 and 3-EMR extraction: Viral load values and appointment attendance data will be extracted from the participants' electronic medical records (EMR) to determine retention and viral suppression outcomes. Clinical data will be entered directly into the Redcap database via a secure online form by graduate research assistants. This will be done at the baseline and 10 month time points.

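### The 10-month chart abstraction comes before the follow-up viral-load window opens, and no later abstraction is stated

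*Combined protocol and SAP*

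**What the plan says.** Three parts of the combined protocol and SAP bear on this point.

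**When charts are read.** Section 5.2, under Data collection, describes research assistants extracting viral loads and appointment attendance and entering them in REDCap, and adds: "This will be done at the baseline and 10 month time points". The RCT overview in section 2.3, having listed the survey times (baseline, about 1 month, 4 and 10 months), says: "We will also abstract clinical data from electronic medical records at these time points". Table 2 in section 4.2 lists viral load for "RCT participants at baseline, post-intervention and 10 months", if available, and refers the reader elsewhere for detail.

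**Which value counts.** Under Clinical Outcome Measures in section 2.3, the value labelled as the 10-month viral load "will be the first value drawn on or after the date that is exactly one year from the beginning of study participation". The same paragraph closes the window: "If this test is done >6 months after the target date, it will be treated as a missing value". The baseline value looks the other way: it is the latest result before participation, and is missing if more than 6 months old.

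**What the 10-month point is counted from.** Section 2.3 counts it from the start of the intervention in the overview, and from study completion under Study visits. The surveys paragraph in section 5.2 counts it from enrollment.

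**The concern.** A rule that looks forward from a target date can be applied only after that date, and can be applied completely only once the window has closed. The plan schedules the reading of the chart for a time when, by its own definition, the window has not opened.

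This is separate from the mismatch between a 10-month label and a one-year target. A sponsor who corrected only that mismatch would still be reading a forward window on about its first day.

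Viral suppression is one of three secondary outcomes and serves Aim 3b. If the schedule is followed, the follow-up value is absent. If staff go back later without a stated date, what they find depends on when each chart was reopened and whether access still exists. The documents leave that access uncertain in three places:

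- Care facility is verified and releases are signed at study visits, the last at 10 months (sections 2.3 and 5.2).
- Participants need not be patients of the study clinic, so outside records depend on those releases (section 3.6).
- Only de-identified datasets are kept once data collection is complete (section 5.5). If collection is taken to end with the 10-month visit, the link to the medical record could be gone before the window closes.

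**Working it through.** The plan states no figure to reproduce. The check is date arithmetic.

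**Inputs.** Target T = 12 months from the start of participation, and window length 6 months (section 2.3, Clinical Outcome Measures). Chart pull A = month 10 if counted from the start of the intervention or from enrollment. A is about month 11 if counted from study completion, assuming that completion means the end of the roughly one-month intervention. Trial size is 120 (section 3.5).

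**Rule.** A value qualifies if drawn between T and T + 6, and can be captured only if drawn by A. The usable overlap runs from T to the earlier of A and T + 6, and is empty if A is before T.

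**As written (T = 12, window 12 to 18).**
- A = 10: the pull is 12 − 10 = 2 months before opening and 18 − 10 = 8 months before closing. No overlap.
- A = 11: 12 − 11 = 1 month before opening and 18 − 11 = 7 months before closing. No overlap.

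Under every stated anchor, 0 of 120 qualifying values exist at the pull.

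**Target moved to month 10 (window 10 to 16).**
- A = 10: the overlap is the single day of month 10, since a draw on the target date qualifies.
- A = 11: the overlap is about 1 month.

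To size this I assumed one routine viral load every 3 to 6 months at a random phase. The documents give no testing interval, so these figures are illustrative. With an average month of 365.25/12 = 30.44 days:

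| Overlap | Tests every 3 months | Tests every 6 months |
|---|---|---|
| One day | 1/(3 × 30.44) = 1.1%, or 1.3 of 120 | 1/(6 × 30.44) = 0.55%, or 0.7 of 120 |
| One month | 1/3 = 33%, or 40 of 120 | 1/6 = 17%, or 20 of 120 |

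The one-day figures would be higher if blood were drawn on the survey day.

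**When the whole window can be read.** Not before T + 6: month 18 with the present target, or month 16 with a 10-month target. Against a pull at month 10, that is 18 − 10 = 8 or 16 − 10 = 6 months later.

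**What is not affected.** The baseline viral load looks backward, so an abstraction at enrollment can find it. Retention is defined within the 10-month study period (section 4.2, Outcome Measures). The primary outcome, the Modified Social Capital Scale, comes from the surveys.

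**The case against.** The best defence is that the 10-month time point is a label, not a calendar date. Section 2.3 supports this: "The goal is to abstract measures that correspond to the 0 month (baseline) and 10 month (long term follow-up) time points", and it concedes that "lab tests (CD4, VL) in the clinical setting may not necessarily be conducted at a time that corresponds to the survey time point". It already gives the 10-month name to a value drawn at one year or later. Record data are dated and can be retrieved afterwards, nothing forbids a later pull, and a rule that accepts values up to 6 months past a target implies that someone looks after the target.

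That reading suits the section 2.3 paragraph. It suits section 5.2 poorly, because the timing there attaches to the act of extraction and entry; the section 2.3 overview likewise ties the act of abstraction to the survey times. Even if the label reading is granted, no section says when the last chart pull happens. The defence does establish that eventual loss of the data is not proven. The count of 0 of 120 holds only if the schedule is followed literally.

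Two stronger readings are tempting and should not be drawn:

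- A reader might infer that the outcome is uncollected for everyone even if the target is moved. With a 10-month target, same-day draws qualify, and about a month of draws qualifies if the visit is counted from study completion.
- A reader might infer bias between arms. Nothing in the documents suggests that charts would be reopened for only some participants or differently by arm.

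The disagreement between schedules should also not be overplayed. The viral-load and CD4 rows of Table 2 differ in little more than punctuation, so a separate post-intervention pull is uncertain. The difference between the section 2.3 overview and section 5.2 is plain.

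**Conclusion.** The conflict between the abstraction date and the viral-load rule stands. Read literally, the only follow-up chart pull precedes the window by 1 to 2 months and its close by 7 to 8, so it yields no qualifying value for any of the 120 participants. This rests on the stated dates alone, apart from the assumption about study completion behind the month-11 case.

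Moving the target to month 10 without changing the abstraction date would still miss most participants: all but about 1 of 120, or all but 20 to 40 of 120 under the study-completion anchor. Those counts depend on the assumed testing interval of 3 to 6 months.

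The consequence is limited to one secondary outcome at one time point, and the remedy is cheap. The change should be made, but the point does not threaten the trial's primary comparison.

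**What to change.** Keep the baseline abstraction. In section 5.2, replace the 10-month abstraction with wording to this effect:

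> A final abstraction is made for every participant after the follow-up viral-load window has closed (target date plus 6 months). It takes all dated viral loads, CD4 tests and HIV visits available at that time. Retention is derived only from events within the 10-month study period. The look-back for nadir CD4 is not limited.

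Then:

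- Use this one schedule in the section 2.3 overview, Clinical Outcome Measures, Table 2 and section 5.2, and settle there whether the target is 10 or 12 months. The final abstraction works with either.
- State in the record release and in sections 5.4 and 5.5 that the release and the ID link file cover the final abstraction date.

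**Cost.** Protocol wording, a release end date, and a data lock about 6 to 8 months later for the last participants, which should be checked against the four-year study period. No visits or tests are added. One weakness remains: care facility is last verified at the 10-month visit, so results from a clinic joined after that may still be missed.

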Study visits: In addition to attending the intervention sessions, participants in both arms will be asked to come to the IDP clinic or Rollins School of Public Health to participate in three study visits: One at baseline before starting the intervention (0 months), immediately after completing the intervention (around 1 month), 4 months and a long term follow-up at 10 months after study completion. The main purpose of these visits will be to complete a survey to measure any change in social capital between the pre- and post-intervention periods. The survey (Appendix F) will also include measures of other theoretically relevant constructs including depressive symptomatology, stigma, and social support. We will also verify the participants' most recent medical care facility and obtain medical record release forms to facilitate abstraction of data on engagement outcomes. Participants will receive tokens of appreciation for each completed study visit (\$25 for the first visit and \$50 for the second) and given MARTA cards at these visits.

Follow-up qualitative interviews: We will conduct n=30 qualitative in-depth interviews in Year 4 with a subset of interested participants who were enrolled in the social capital intervention arm, in order to understand their experiences in the program and solicit feedback for future implementation of the intervention. Procedures and analytic plans will be as described in the Phase 1 interviews above. Participants will sign a separate informed consent to participate, and will receive an additional \$25 token of appreciation for their time if they choose to do so. The maximum total amount for tokens of appreciation for participants who do all sessions is \$175.

2.4 Audience and stakeholder participation: Our study follows a community-based participatory approach designed to ensure stakeholder participation. First, we will conduct interviews with community stakeholders to inform our understanding of social capital in our target population. Second, we will create a youth community advisory board (YCAB) designed specifically to engage members of the community at each step of the process. Finally, at the end of the project, we will plan to disseminate findings not only in academic publications but also in a community forum.

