3.2.3 Exclusion Criteria

- Age $<$ 18 years or \geq 30 years
- Unwilling or unable to provide written informed consent
- Enrollment in one phase of the study is an exclusion criteria for enrollment in other phases

3.3 Justification for inclusion/exclusion criteria: We are focusing exclusively on YBMSM in this study due to the disproportionate impact of HIV in this population, as detailed in the literature review above. We are aiming to develop an intervention that is culturally and developmentally appropriate, and as such are limiting our enrollment to this target population.

3.4 Estimated number of participants: We plan to enroll 180 total participants (120 in the randomized controlled trial and 60 in preliminary interviews).

3.5 Sampling, including sample size and statistical power:

Based on our MSCS scale characteristics in our previous online survey study (mean 26.6, standard deviation 7.0), we can estimate that a sample size of n=106 (n=53 in each of the intervention and control groups) would allow us to detect approximately a 15% increase in social capital attributable to our intervention (using 80% statistical power). For the RCT, we will therefore aim to recruit n=120 patients (accounting for some attrition): based on our team's previous work in the same geographic area, we believe this to be a feasible number of YBMSM to recruit during the specified time period from our IDP clinic and community partners.

Table 1. Power calculation

Control Patients	Intervention Patients	Control SC Mean	Intervention SC Mean	Detectable Effect Size	Detectable Percent Increase in SC
31	31	26.6	31.9	0.75	20%
39	39	26.6	31.3	0.67	17.5%
50	50	26.6	30.7	0.58	15.4%
53	53	26.6	30.6	0.57	15%
77	77	26.6	29.9	0.47	12.5%
114	114	26.6	29.3	0.38	10%

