Phase 2 and 3-surveys: In addition to attending the intervention sessions, participants in both arms will be asked to come to the IDP clinic to participate in three study visits: One at baseline before starting the intervention (0 months), immediately after completing the intervention (around 1 month), 4 months, and a long term follow-up at 10 months after enrollment. The main purpose of these visits will be to complete a survey using the Research Electronic Data Capture (Redcap) online survey platform on an electronic tablet. The Redcap survey will contain our MSCS and will be used to measure change in social capital between the pre- and post-intervention periods. We will also verify the participants' most recent medical care facility (since the last visit) and obtain the participants' signatures on medical record release forms to facilitate abstraction of data on engagement outcomes.

5.3 Data Entry, Editing and Management:

All survey and clinical data will be entered into a password protected, HIPAA compliant RedCap database. The database will be accessible only to the study team. Any subsequent datasets that are exported for analysis will be stripped of identifying information and will only be linked by a participant ID number.

In terms of identifying discrepancies, some of this will be done prospectively by building quality checks into the Redcap data collection system—for example, if certain data do not line up between the baseline and follow up surveys (e.g. participant's date of birth), participants will be prompted to re-enter their answers to that question. Once per month, data will be reviewed in more detail for potential errors. We will ask our biostatistician to conduct descriptive analyses in order to help us identify outliers and return to the original data source as needed to confirm outlying values.

Qualitative interviews will be transcribed verbatim. Identifying information (names) will be taken out at the time of transcription. Files will be kept in a secured shared drive (Emory Box or equivalent) for access by study staff only.

5.4 Provisions for protecting privacy:

Breach of privacy is a concern in this study as identifying information/personal health information will be collected as part of the data collection process. Additionally, efforts to

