5.8 Intermediate reviews and analyses

As this is not a clinical trial with potential for physical harm, it is unlikely that any interim analyses of efficacy (significant differences in social capital improvement between the two arms) would cause us to halt the trial prematurely (either for no benefit or significant benefit from the social capital intervention). However, there are other reasons to conduct interim reviews and analyses as the trial progresses; namely: to review comparability of the intervention and control arms, to review retention and participant accrual rates, and to review quality of the data. We will plan to review our enrollment data on a weekly basis; our project coordinator will generate reports of numbers enrolled and rate of completing follow-up visits and present them at our weekly team meeting. Our biostatistician will also generate summaries of our enrollment, retention, and baseline survey responses every 3 months. Additional analyses may be undertaken for the purpose of presentation in national and international scientific meetings.

5.9 Limitations of study:

There are several limitations to this study. Recruitment and retention have the potential to be challenging among YBMSM living with HIV. In terms of initial recruitment, subjects who are newly diagnosed or re-engaging in care may decline participation due to challenges coping with new information, denial and/or grief in response to their new diagnosis. Experienced personnel and dedicated coordinators will be used to maximize recruitment. We are also planning to recruit from a wide range of venues including the Grady IDP clinic and our partnering community-based organizations. If enrollment is still inadequate, which is unlikely, we also have relationships with other clinical sites in Atlanta that care for HIV-positive YBMSM aged 18-29 (the Emory Midtown Hospital HIV clinic, Atlanta Veterans Administration Hospital, Fulton County Health Department) and could look into expanding recruitment to those sites.

5.10 Identifying, managing, and reporting adverse events:

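### Baseline MSCS is collected but never used as a covariate, and the sample size in 3.5 does not match the improvement contrast worded elsewhere

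*Combined protocol and SAP*

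**What the plan says.** Table 2 (4.2) names social capital, measured by the MSCS, as the primary outcome and schedules it for RCT participants at 0, 1, 4 and 10 months. A baseline score is therefore planned for everyone randomised.

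Where the plan describes how those scores will be used, the language is of change:

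- Section 2.3, study visits: participants "complete a survey to measure any change in social capital between the pre- and post-intervention periods".
- Section 5.2, data collection for the Phase 2 and 3 surveys: the survey "will be used to measure change in social capital between the pre- and post-intervention periods".
- Section 5.8: interim efficacy is explained in a parenthesis as "significant differences in social capital improvement between the two arms".

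The sample size in 3.5 has a different basis. It takes a mean of 26.6 and an SD of 7.0 from an earlier online survey and states that 53 per arm can "detect approximately a 15% increase in social capital attributable to our intervention" ("using 80% statistical power"). Table 1 shows this as 26.6 against 30.6, effect size 0.57. It gives no alpha, no SD of change and no baseline/follow-up correlation.

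Section 5.2.1, on quantitative analysis, repeats the cross-sectional plan of Phase I Part 1c. It has no comparison of MSCS between arms and no baseline adjustment.

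**The concern.** The contrast put into words and the contrast that was sized are different quantities. A difference in improvement has a variance that depends on how strongly baseline and follow-up scores correlate. A difference between two follow-up means, which is what Table 1 uses, does not. The 80% in 3.5 therefore does not carry over automatically to the contrast in 5.8.

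Neither version makes good use of the month 0 score. A follow-up-only comparison discards it. A raw change score subtracts it in full, which adds noise when the correlation is low and overcorrects a chance difference between arms at baseline. Using it as a covariate avoids both problems and needs no new data. Leaving the choice open also means that it could be made after the data are seen.

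**Working it through.** **Inputs.** From 3.5: control mean 26.6, intervention mean 30.6, difference 4.0, SD 7.0, 53 evaluable per arm, 60 per arm enrolled. Assumed, because the documents do not say: two-sided alpha 0.05, the same SD at both visits, independent observations. The baseline/follow-up correlation ρ is not given, so a range is shown.

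**Reproducing the plan's figure.** The effect size is 4.0/7.0 = 0.571, which matches Table 1's 0.57. The table therefore uses the SD of a single score. A two-sample t-test at two-sided 0.05 needs 50 per arm for 80% power, and 53 per arm gives 83.0%. The stated 53 is thus not reproduced at 0.05 but is slightly conservative. A two-sided alpha of 0.04 returns all six rows of Table 1 (31, 39, 50, 53, 77, 114), though the plan does not state that alpha.

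**Variance of each possible contrast, relative to 7.0².**

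- Follow-up only: 1
- Change from baseline: 2(1−ρ)
- Follow-up with baseline as covariate: 1−ρ² = (1−ρ)(1+ρ)

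Because 1+ρ is at most 2, the third factor never exceeds the second. Because ρ² is at least 0, it never exceeds the first.

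**Power at 53 per arm, and n per arm for 80% power** (difference 4.0, two-sided 0.05, no clustering):

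| ρ | SD of change | Power, follow-up only | Power, change | Power, baseline as covariate | n, change | n, covariate |
|---|---|---|---|---|---|---|
| 0.2 | 8.85 | 83.0% | 63.5% | 84.5% | 78 | 48 |
| 0.3 | 8.28 | 83.0% | 69.3% | 86.3% | 69 | 45 |
| 0.4 | 7.67 | 83.0% | 75.8% | 88.9% | 59 | 42 |
| 0.5 | 7.00 | 83.0% | 83.0% | 92.0% | 50 | 38 |
| 0.6 | 6.26 | 83.0% | 90.3% | 95.4% | 40 | 32 |
| 0.7 | 5.42 | 83.0% | 96.4% | 98.3% | 30 | 26 |

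**Correlation at which a change score reaches 80%.** With 53 per arm the SD of change may be at most 7.28, so ρ must be at least 1 − 7.28²/(2 × 49) = 0.459. With all 60 per arm evaluable the limit is 7.756 and ρ must be at least 0.386. With 53 per arm at two-sided 0.04 the limit is 7.039 and ρ must be at least 0.494.

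**Chance imbalance.** With 53 per arm the baseline difference between arms has standard error 7.0 × √(2/53) = 1.36 points, about a third of the 4.0-point target. At ρ = 0.4, an imbalance of that size shifts the change contrast by (1−0.4) × 1.36 = 0.8 points and the follow-up-only contrast by 0.4 × 1.36 = 0.5 points. Baseline adjustment removes this.

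**The case against.** The strongest reply is that nothing in the plan specifies a change-score test. The wording in 2.3 and 5.2 says what the survey is for. The wording in 5.8 is a parenthesis in a sentence about why interim efficacy results are unlikely to stop the trial. Everyday talk of change and improvement is compatible with a baseline-adjusted model. Table 1 is the only quantified arm comparison, and read as a comparison of follow-up means it has 83% power at any correlation. This stands. A reader might infer that the plan has chosen raw change scores and that its 80% power therefore fails; the documents support neither step.

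The correlation is also unknown. The only reliability figure, an alpha of 0.88 in Part 1c, comes with no retest interval. No primary time point is fixed, so the relevant gap could be about 1 month or 10. Above 0.5 a change score has more power than Table 1's comparison. This stands too, and it is why a range is given.

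A reader might also argue that baseline imbalance is likely because there are only about six groups per arm. Section 2.3 describes allocating participants to arms, with each arm then divided into groups, so the argument has to rest on 53 to 60 people per arm.

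Finally, delivery in groups of about 10 lowers every absolute figure. With an assumed intraclass correlation of 0.05 the design effect is 1 + 9 × 0.05 = 1.45, and follow-up-only power at 53 per arm falls to about 67%. That is a separate problem.

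None of these points argues against baseline adjustment. It is at least as powerful as a change score at any correlation and, apart from one degree of freedom, no worse than follow-up alone.

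**Conclusion.** The point holds as a conditional one. The plan collects a baseline score on its primary outcome, gives it no role as a covariate, words the arm comparison as improvement, and sizes the trial on something else.

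If change scores were compared with 53 per arm, 80% power would need a correlation of at least about 0.46. That threshold moves to about 0.39 with 60 completers per arm and to about 0.49 at two-sided 0.04. Whether the true correlation lies above or below it cannot be determined from the documents.

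At correlations of 0.3 to 0.6, baseline adjustment gains about 5 to 17 percentage points of power over a change score and about 3 to 12 over follow-up alone. These figures assume a difference of 4.0, SD 7.0 at both visits, two-sided 0.05 and no clustering. The case for the change is that it is a nearly free improvement under any reading of the plan, not that the stated power has been shown to fail.

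**What to change.** In 5.2.1, state that the between-arm comparison of follow-up MSCS includes baseline MSCS as a covariate. This can be an ANCOVA, or the baseline term in a repeated-measures model that also accounts for intervention group. Keep mean change by arm as a descriptive summary only, and align the wording in 2.3, 5.2 and 5.8 with this.

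In 3.5, state the alpha. Say that Table 1 uses the unadjusted single-time SD of 7.0 and does not apply to change scores. Add that baseline adjustment multiplies the variance by 1−ρ², with ρ unknown and shown as a range: before clustering, power at 53 per arm is 86% to 95% for ρ of 0.3 to 0.6, against 83% unadjusted.

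The cost is wording and one degree of freedom. No new data, visits or participants are needed. The change should be made before outcome data are compared by arm.
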